Missing data at Week 16 that are not preceded by an intercurrent event, and any data after an intercurrent event will be imputed as non-responders.

The statistical hypothesis for the ACR50 response at Week 16 is that the conditional odds ratio for ACR50 response in the bimekizumab treatment compared with placebo treatment is equal to 1.

A logistic regression model will be used to assess the treatment effect on ACR50 response at Week 16. The model will include a fixed effect for treatment. The suitability of including the randomization stratification variables, region and bone erosion at Baseline will be assessed and will be added to the model if appropriate. Comparisons will be made using the 2-sided Wald test at a significance level of  $\alpha=0.05$  (ie,  $H_1$  in [Figure 14-1](#)). The odds ratio versus placebo, p-value, and the 95% CI will be calculated.

---

Any use of prohibited or rescue medications through Week 16 would constitute an important protocol deviation which would be accounted for when the sensitivity analysis based on the PPS is performed (see [Section 14.3.1.1.1](#)).

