#### **14.3.1.2    Analysis of the secondary efficacy variables**

The secondary efficacy variables will be analyzed for all subjects in the RS.

All binary variables that are part of the testing hierarchy are given below:

- PASI90 responders at Week 16 will be analyzed to evaluate the composite estimand. The composite estimand combines the clinically meaningful improvement from Baseline in PASI90 response and not discontinuing treatment early.
- The proportion of subjects achieving MDA status at Week 16 will be analyzed to evaluate the composite estimand. The composite estimand combines (1) achieving the MDA status with (2) not discontinuing treatment early.
- The proportion of subjects with enthesitis at Baseline achieving enthesitis-free status at Week 16 will be analyzed to evaluate the composite estimand. The composite estimand combines (1) achieving the enthesitis-free status with (2) not discontinuing treatment early. For this analysis, the PA0010 and PA0011 data will be pooled.

---

- The proportion of subjects with dactylitis at Baseline achieving dactylitis-free status at Week 16 will be analyzed to evaluate the composite estimand. The composite estimand combines (1) achieving the dactylitis-free status with (2) not discontinuing treatment early. For this analysis, the PA0010 and PA0011 data will be pooled.

The statistical hypothesis for the binary variables at Week 16 is that the conditional odds ratio for binary variables in the bimekizumab treatment compared with placebo treatment groups is equal to 1.

The binary variables will be analyzed using the same analysis methods and estimand approach as used for the primary variable ([Section 14.3.1.1](#)).

If appropriate ie, where the outcome variable (eg, PASI90 response) is an assessment of skin/dermatological manifestations of PsA the fitted model will exclude the fixed term bone erosion at Baseline.

All continuous variables that are part of the testing hierarchy are given below:

- Change from Baseline in HAQ-DI at Week 16
- Change from Baseline in the SF-36 PCS score at Week 16
- Change from Baseline in vdHmTSS at Week 16

Continuous variables will be analyzed to evaluate the hypothetical estimand as defined below:

1. Population = Subjects enrolled according to the protocol-specified inclusion/exclusion criteria and randomized to IMP.
2. Subject level outcome = variable as stated in [Section 4.2.1](#)

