## **14.9 Determination of sample size**

Approximately 840 subjects will be randomly assigned in a 3:2:1 ratio to the following treatment groups: bimekizumab 160mg sc Q4W (420 subjects), placebo (280 subjects), adalimumab 40mg sc Q2W (140 subjects).

The primary efficacy analysis is based on the bimekizumab dose versus placebo for ACR50 response at Week 16. It is planned that only descriptive summaries will be provided for the adalimumab reference arm. No statistical comparisons will be made between adalimumab and the other treatment groups.

All sample size and power calculations were done at a significance level of 0.05.

All sample size and power calculations were performed using the software nQuery Advisor® 7.0.

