### **14.9.2 Power calculations for secondary endpoints**

The assumptions for power calculations of the secondary endpoints included in the hierarchy, and for which supporting data exists, are based on the interim results of the Phase 2b

---

bimekizumab study PA0008 and the FUTURE 1, FUTURE 2, FUTURE 5, and SPIRIT P1 studies. All power calculations for binary endpoints were performed using a 2-sided 2-sample Chi-square test with continuity correction (Fleiss et al, 1980). All power calculations for continuous endpoints were performed using a 2-sided 2-group Satterthwaite t-test (Moser et al, 1989).

For the PASI90 response at Week 16, the bimekizumab 160mg Q4W treatment response at Week 12 is 45% (n=20) in the TNF $\alpha$ -naïve population of PA0008 at Week 12 and 46% (n=28) at Week 12 in the mixed TNF $\alpha$  exposure population. The placebo PASI90 response at Week 16 is based on the subgroup analyses of TNF $\alpha$  therapy-naïve subjects in PA0008 (9.1% at Week 12; n=22), FUTURE 2 study (9.7% at Week 24; n=63), and SPIRIT P1 study (1.5% at Week 12; n=67). Therefore, a placebo PASI90 response rate of 10% is assumed. With those assumptions, the study has >99% power to detect a true treatment difference at an assumed 60% of subjects with BSA  $\geq$ 3% of the planned sample size.

For change from Baseline in HAQ-DI at Week 16, the between treatment differences of the change from Baseline in HAQ-DI of in the mixed TNF $\alpha$  exposure population of the PA0008 at Week 12 were used. The bimekizumab 160mg Q4W treatment group mean change from Baseline in HAQ-DI at Week 12 of -0.37, SD=0.47 (n=41) versus placebo mean change from Baseline in HAQ-DI at Week 12 of -0.13, SD=0.50 (n=42). With those assumptions, the study has >99% power to detect a true treatment difference of -0.24 at the planned sample size.

For change from Baseline in PCS of SF-36 at Week 16, the between treatment differences of the change from Baseline in PCS of SF-36 of the TNF $\alpha$ -naïve population of FUTURE 2 study (Kavanaugh et al, 2016) at Week 24 were used. The bimekizumab 160mg Q4W treatment group assumes the secukinumab 150mg treatment group mean change from Baseline in SF-36 PCS at Week 24 of 7.91, SD 7.38 (N=63) versus placebo mean change from Baseline in SF-36 PCS at Week 24 of 2.08, SD 9.51 (N=63). With those assumptions, the study has >99% power to detect a true treatment difference of 5.83 at the planned sample size.

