**Table 14–1: Treatment effect by elevated hs-CRP and/or bone erosion at Baseline for secondary efficacy analyses**

Subjects with elevated hs-CRP and/or bone erosion at Baseline	Treatment difference/standard deviation	
	Treatment effect = -0.3 SD=0.72 vs 0.71	Treatment effect = -0.35 SD=0.81 vs 0.93
20%	67	62
25%	76	72
30%	84	79
35%	89	85
40%	92	89
45%	95	92
50%	96	95

hs-CRP=high sensitivity C-reactive protein; SD=standard deviation

For enthesis free-state at Week 16, enthesis resolution data from the FUTURE 5 study at Week 16 were used to estimate the bimekizumab 160mg Q4W treatment and placebo groups. In FUTURE 5 The treatment effect estimate from the secukinumab 150mg treatment group at Week 16 was 55% (n=141) and the placebo group estimate was 36% (n=192). Assuming a BKZ response of 55% and a placebo rate of 39% and having 25% of subjects with Baseline enthesis the pooled PA0010/PA0011 the studies have a 69% power to detect a true treatment difference of 16% (odds ratio 1.91).

For dactylitis-free state at Week 16, dactylitis resolution data of the FUTURE 5 study (Mease et al, 2018) at Week 16 were used to estimate the bimekizumab 160mg Q4W treatment and placebo groups. The treatment effect estimate from the secukinumab 150mg treatment group at Week 16 of 56% (n=103) is assumed versus a placebo group estimate of 32% (n=124). With those assumptions and having 11% of subjects with Baseline dactylitis, the pooled PA0010/PA0011 studies have a 66% power to detect a true treatment difference of 24% (odds ratio 2.71).

Treatment difference in change from Baseline in vdHmTSS at Week 16 in the overall population is estimated using the data from the FUTURE 5 study in a mixed TNF $\alpha$  exposure population. The bimekizumab 160mg Q4W group treatment difference compared to placebo is estimated to be the same as the difference in change from Baseline in vdHmTSS at Week 16 between the secukinumab 150mg group and placebo which is 0.42, assuming a SD of 1.13 for bimekizumab and SD=2.44 for placebo. With these assumptions the study has 76% power to detect a treatment difference of 0.42 in the planned sample size.

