**Specific changes:**

Protocol section impacted	Key components of previous protocol text	Key components of revised protocol text	Rationale
Change 1: Administrative section			
Study contact details	████████ UCB Celltech Ltd [name] ████████	████████ UCB Celltech Ltd [name] ████████	The Sponsor Study Physician has changed.
	████████ UCB BIOSCIENCES Inc. [name] UNITED STATES ████████	████████ UCB BIOSCIENCES GmbH [name] 40789 Monheim GERMANY ████████	The Clinical Project Manager has changed.
Change 2: Abbreviation added			
List of abbreviations	Abbreviations and definitions added for the following: LN, PsARC, PASDAS		Abbreviations used in text.
Change 3: Updated text in clinical studies section			
Section 2.2.2.1	The list of completed studies was updated consistent with the current bimekizumab IB.		More studies have completed, and additional studies have started, since the last protocol amendment.
Section 2.2.2.2	The list of ongoing studies was updated consistent with the current bimekizumab IB.		

Protocol section impacted	Key components of previous protocol text	Key components of revised protocol text	Rationale
Change 4: Updated 2 secondary efficacy variables			
Section 4.2.1	
 
• Dactylitis-free state based on the Leeds Dactylitis Index (LDI) at Week 16 in the subgroup of subjects with dactylitis at Baseline
 
• Change from Baseline in the Leeds Enthesitis Index (LEI) at Week 16 in the subgroup of subjects with enthesitis at Baseline
 
	
 
• Change from Baseline Enthesitis-free state in the Leeds Enthesitis Index (LEI) at Week 16 in the subgroup of subjects with enthesitis at Baseline in the pooled population of PA0010 and PA0011
 
• Dactylitis-free state based on the Leeds Dactylitis Index (LDI) at Week 16 in the subgroup of subjects with dactylitis at Baseline in the pooled population of PA0010 and PA0011
 
	
In order to provide more clinically interpretable results for dactylitis and enthesitis endpoints across a more robust mixed population (TNF-inadequate responders and bDMARD-naïve), the endpoints of dactylitis free-state and enthesitis free-state will be analyzed using a pooled PA0010 and PA0011 population.

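### The two pooled PA0010/PA0011 tests take over a single-study model with no study term, so their result could be confounded by study if PA0011 has a different allocation ratio and different placebo rates

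*Protocol*

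**What the plan says.** Protocol section 14.3.1.2 lists four binary variables in the testing hierarchy. For two of them, enthesitis-free and dactylitis-free state at Week 16, it adds: "For this analysis, the PA0010 and PA0011 data will be pooled". It then sets the method for all four together: "The binary variables will be analyzed using the same analysis methods and estimand approach as used for the primary variable".

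That method is in section 14.3.1.1. It is a logistic regression with a two-sided Wald test, of which the text says "The model will include a fixed effect for treatment". Region and bone erosion, the PA0010 stratification factors, are assessed for suitability and added if appropriate. The only adaptation in section 14.3.1.2 is to drop bone erosion for skin outcomes. Neither section names study as a factor.

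Section 2.2.2.2 describes PA0011 as a randomised, placebo-controlled trial in its own right. The rationale for Change 4 in section 18.3 (Protocol Amendment 2) says that pooling gives results "across a more robust mixed population (TNF-inadequate responders and" bDMARD-naïve subjects).

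Section 4.3.1 also plans both endpoints for PA0010 alone, among the other efficacy variables.

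**The concern.** Randomisation makes the arms comparable within each trial. It does not do so across two trials put together unless both allocate bimekizumab and placebo in the same ratio or have the same underlying response rates. If both conditions fail, one trial supplies a larger share of one arm and also has a different background rate. The crude pooled comparison then carries part of the difference between the trials.

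Region and bone erosion, even if kept, do not stand in for study.

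Two confirmatory tests are at stake. Their stated power is 69% (enthesitis) and 66% (dactylitis) in section 14.9.2, and section 14.3.1 stops testing at the first hypothesis that is not rejected. A shift in either direction could therefore decide one of these claims and whether anything after it is tested.

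**Working it through.** **Inputs from the protocol**
- Significance level (section 14.9): "All sample size and power calculations were done at a significance level of 0.05".
- Power method (section 14.9.2): "All power calculations for binary endpoints were performed using a 2-sided 2-sample Chi-square test with continuity correction".
- PA0010 arms (section 14.9): "bimekizumab 160mg sc Q4W (420 subjects), placebo (280 subjects), adalimumab 40mg sc Q2W (140 subjects". Bimekizumab to placebo is 420:280 = 3:2.
- Enthesitis (section 14.9.2): "Assuming a BKZ response of 55% and a placebo rate of 39% and having 25% of subjects with Baseline enthesis", with a stated odds ratio of 1.91.
- Dactylitis (section 14.9.2): 56% against 32%, 11% of subjects affected.
- PA0011 size, allocation and placebo rates: not given, so assumed below.

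**Step 1: the plan's own figures.** The enthesitis odds ratio is (0.55/0.45)/(0.39/0.61) = 1.912, as stated. PA0010 alone contributes 0.25 × 420 = 105 and 0.25 × 280 = 70 subjects with enthesitis. The continuity-corrected power is then 48%; for dactylitis it is 45%. The stated 69% and 66% depend on PA0011, so they cannot be reproduced from the document. They are plausible: adding 350 PA0011 subjects at 1:1 gives 68.9% and 66.8%, and adding 400 at 2:1 gives 69.0% and 66.7%.

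**Step 2: crude pooled odds ratio for enthesitis.** Assume 400 PA0011 subjects in the two arms, so 0.25 × 400 = 100 with enthesitis. Give both trials the same within-study odds ratio and set the PA0011 placebo rate 5 to 15 points below 39%.

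Example, ratio 3:1 and 15 points lower:
- PA0011 placebo rate 0.24; odds 0.24/0.76 = 0.3158.
- PA0011 bimekizumab odds 1.912 × 0.3158 = 0.604; rate 0.604/1.604 = 0.3764.
- Bimekizumab responders: 105 × 0.55 + 75 × 0.3764 = 85.98 of 180.
- Placebo responders: 70 × 0.39 + 25 × 0.24 = 33.3 of 95.
- Crude odds ratio: (85.98/94.02)/(33.3/61.7) = 1.69.

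Example under no effect, same setting: bimekizumab 105 × 0.39 + 75 × 0.24 = 58.95 of 180; placebo 33.3 of 95; crude odds ratio (58.95/121.05)/(33.3/61.7) = 0.90.

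| PA0011 ratio | Crude OR, true OR 1.912 (5 to 15 points lower) | Crude OR, no effect |
|---|---|---|
| 1:1 | 1.947 to 2.005 | 1.020 to 1.065 |
| 3:2 | 1.908 to 1.880 | 1.000 |
| 2:1 | 1.882 to 1.798 | 0.986 to 0.957 |
| 3:1 | 1.847 to 1.695 | 0.968 to 0.902 |

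The directions reverse if the PA0011 placebo rate is higher.

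**Step 3: effect on the test.** Simulation used 20,000 trials per scenario, 400 PA0011 subjects, bimekizumab shares of 50% to 75%, and PA0011 placebo rates from 20 points below to 10 points above those in PA0010. It compared a treatment-only logistic model with one that adds study.

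| | Treatment only | Treatment + study |
|---|---|---|
| Two-sided type I error, both endpoints | 0.044 to 0.077 | 0.049 to 0.053 |
| Enthesitis odds ratio (true 1.91) | 1.61 to 2.02 | 1.91 to 1.93 |
| Dactylitis odds ratio (true 2.70) | 2.14 to 2.86 | 2.75 to 2.78 |
| Enthesitis power (Wald, uncorrected) | 0.44 to 0.81 | 0.67 to 0.75 |

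The odds ratios are crude values for the treatment-only model and medians for the model with study. For enthesitis without the study term, the error in the direction favouring bimekizumab was 0.005 to 0.048 against a nominal 0.025.

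**The case against.** The strongest reply is that the statistical analysis plan would settle this. Section 14 says that plan gives more detail, the covariate list is partly open, and the hypothesis concerns a conditional odds ratio, so some adjustment is expected. This has weight: the protocol omits study but does not exclude it, and a reader should not infer that it rules out stratification by study. Even so, it does more than stay silent. It pools two trials and assigns them, by cross-reference, a model whose optional terms are the PA0010 stratification factors.

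A reader might also infer that the pooled tests definitely break the randomisation or inflate the false-positive rate. The documents do not support that. Bias under no effect needs both a PA0011 ratio other than 3:2 and different placebo rates, and neither is given. The amendment shows that the populations differ, not that their enthesitis or dactylitis rates do. With lower PA0011 placebo rates, only the 1:1 case raises the risk of a false efficacy claim; 2:1 and 3:1 cost power.

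Nor is the drop from 1.91 to 1.88 at 3:2 a bias. The odds ratio is non-collapsible, so leaving study out targets a slightly different quantity. The simulated test at 3:2 was at most slightly conservative, with two-sided error of 0.044 at the lowest.

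Finally, the PA0010-alone analyses will give an estimate protected by randomisation. That helps interpretation, but they lie outside the hierarchy and do not repair the two confirmatory tests.

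**Conclusion.** The point holds in conditional form. The protocol carries a single-study model over to pooled data from two separately randomised trials without adding study. The pooled effect is confounded if PA0011 differs from PA0010 in both allocation ratio and placebo rate. Under the Step 2 assumptions, the crude enthesitis odds ratio is about 1.7 to 2.0 against 1.91, and 0.90 to 1.07 with no effect. No direction can be asserted, and at 3:2 the null comparison is unbiased.

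The stated power figures are not shown to be wrong. The primary endpoint is unaffected. Later hypotheses are affected only through the stopping rule. All sizes rest on assumed PA0011 numbers, ratios and rates, and on a common within-study odds ratio.

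**What to change.** State in section 14.3.1.2 that the pooled enthesitis-free and dactylitis-free tests include study as a fixed effect in the logistic model, or are stratified by study. Report each study's estimate and the treatment-by-study estimate descriptively beside the pooled result.

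The cost is a sentence or two and one model term. No further data are needed. In the scenarios simulated, the study term kept the two-sided error between 0.049 and 0.053 whatever the PA0011 ratio, so it can be adopted without first settling whether confounding would arise.

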The overall study design consists of a Screening Period ( $\geq 14$  days to  $\leq 35$  days), a 16-week placebo-controlled Double-Blind Treatment Period, a 36-week Active Treatment-Blind Period, and a Safety Follow-Up (SFU) Visit 20 weeks after the final dose of investigational medicinal product (IMP) (for subjects not entering the extension study or who discontinue early, including those withdrawn from IMP). The maximum study duration per subject will be up to 73 weeks.

It is planned to enroll a minimum of 45% of subjects who are positive for elevated high sensitivity C-reactive protein (hs-CRP  $\geq 6$ mg/L) and/or who have at least 1 bone erosion at Screening.

During the Double-Blind Treatment and Active Treatment-Blind Periods, permitted rescue therapy after Week 16 is described in [Section 5.4](#). Subjects' permitted background medications may be changed if the subject is not responding as per Investigator assessment.

Subjects completing Week 52 are eligible for enrollment in an extension study where all subjects will receive bimekizumab.

Approximately 840 subjects will be randomly assigned in a 3:2:1 ratio (stratified by region and bone erosion [0,  $\geq$ 1]) to the following treatment groups: bimekizumab 160mg sc Q4W (420 subjects), placebo (280 subjects), and adalimumab sc 40mg every 2 weeks (Q2W) (140 subjects). The planned number of study sites is approximately 150.

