### **5 STUDY DESIGN**

#### **5.1 Study description**

This is a Phase 3, multicenter, randomized, double-blind, placebo-controlled, active-reference study to evaluate the efficacy and safety of bimekizumab in subjects with active PsA. To be eligible to participate in this study, subjects must be adults with a diagnosis of active PsA based on the CASPAR criteria and have active disease with TJC  $\geq 3$  and SJC  $\geq 3$ . It is planned to enroll a minimum of 45% of subjects who are positive for elevated hs-CRP (hs-CRP  $\geq 6$ mg/L) and/or who have at least 1 bone erosion at Screening.

Subjects should not have previously been treated with any biologic drugs for PsA or PSO. Detailed inclusion and exclusion criteria are presented in [Section 6.1](#) and [Section 6.2](#), respectively.

The study will include 3 periods: a Screening Period ( $\geq 14$  days to  $\leq 35$  days), a Treatment Period (52 weeks), and a Safety Follow-up Period (20 weeks after the final dose of IMP). The Treatment Period will consist of a 16-week Double-Blind Treatment Period followed by a 36-week Active Treatment-Blind Period. Permitted rescue therapy changes after Week 16 are described in [Section 5.4](#). The maximum study duration per subject will be up to 73 weeks.

Eligible subjects will be randomized 3:2:1 (stratified by region and bone erosion [0,  $\geq 1$ ]) to receive 1 of 3 blinded treatments (bimekizumab 160mg sc Q4W, placebo, or active-reference [adalimumab 40mg sc Q2W]) and will remain on their allowable background medication. Details of the Treatment Period are provided in [Section 5.3](#).

---

Subjects completing Week 52 and meeting eligibility criteria are eligible for enrollment in an extension study to continue to receive bimekizumab.

An interim analysis of all available data (including efficacy, safety, and PK) will be undertaken after all randomized subjects have completed 24 weeks of treatment or have withdrawn from IMP or the study. The purpose of this analysis is to perform a comprehensive evaluation of all available data for the 3 treatment arms to prepare a regulatory submission for a marketing authorization application based on this analysis.

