## **5.2 Screening Period/Baseline**

The Screening Period will last for a minimum duration of 14 days and a maximum duration of 35 days and will involve obtaining laboratory data and verifying that the doses of nonsteroidal anti-inflammatory drugs (NSAIDs), or permitted DMARDs, if used to treat PsA, are stable. The Screening Period will also enable washout of any medications not permitted for use during the study.

During the Screening Period, X-rays of hands and feet will be assessed for bone erosion and used for the stratification of subjects at Baseline (Day 1).

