## **14.3 Planned efficacy analyses**

### **14.3.1 Analysis of the primary and secondary efficacy variables**

A fixed sequence testing procedure will be applied for the primary and selected secondary variables. The testing procedure will control the family-wise type-I-error and will account for multiplicity. The family-wise error will be set to  $\alpha=0.05$  (2-sided).

For each test, on each binary efficacy endpoint, the null hypothesis is that the conditional odds ratio is equal to one.

$H_0: OR_{T1T2} = 1$

The alternative hypothesis is that the conditional odds ratio is not equal to one.

$H_A: OR_{T1T2} \neq 1$

For each test on each continuous efficacy endpoint, the null hypothesis is that there is no difference between treatment groups.

$H_0: T_1 - T_2 = 0$

The alternative hypothesis is that there is a difference between treatment groups.

$H_A: T_1 - T_2 \neq 0$

[figure not shown]
For the primary and secondary variables, the primary comparison is the bimekizumab 160mg sc Q4W vs placebo. Point estimates and 95% confidence intervals (CI) will be calculated.

No formal statistical comparisons will be made with the adalimumab 40mg sc Q2W treatment group.

The testing starts with  $H_1$ . If  $H_1$  can be rejected at  $\alpha=0.05$  (2-sided), the corresponding  $\alpha$  will be passed on to the next test in the sequence and testing will continue. The testing will be stopped if a hypothesis cannot be rejected at  $\alpha=0.05$  (2-sided).

The fixed sequence testing procedure of primary and secondary efficacy endpoints is shown in Figure 14-1.

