**Has been changed to:**

(in the revised figure [below], the “CfB HAQ-DI at W16 superior to placebo” has moved to the H2 position from the H3 position and the “PASI90 response at W16 superior to placebo” has moved to the H3 position from the H2 position.)

ACR=American College of Rheumatology; BKZ=bimekizumab; CfB=change from Baseline; H=hypothesis; HAQ-DI=Health Assessment Questionnaire—Disability Index; hs-CRP=high sensitivity C-reactive protein; LEI=Leeds Enthesitis Index; MDA=Minimal Disease Activity; PASI=Psoriasis Area and Severity Index; PCS=Physical Component Summary; Q4W=every 4 weeks; SF-36=Short-Form 36-item Health Survey; vdHmTSS=Van der Heijde modified Total Sharp Score; W=Week

\* It is planned to enroll a minimum of 3545% of subjects ~~with~~**who are positive for** elevated hs-CRP (hs-CRP  $\geq 6\text{mg/L}$ ) and/or ~~with~~**who have** at least ~~one~~1 bone erosion ~~at Screening~~(hs-CRP  $\geq 6\text{mg/L}$  and/or erosion positive).

\*\*Based on the overall population

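### The PASI90 model leaves out bone erosion, a randomisation stratum: a small analyse-as-randomised weakness, not a loss of error control

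*Protocol*

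**What the plan says.** **Randomisation.** Protocol Section 5.1 states: "Eligible subjects will be randomized 3:2:1 (stratified by region and bone erosion" (0, ≥1). Section 5.2 says that Screening X-rays of hands and feet "will be assessed for bone erosion and used for the stratification of subjects at Baseline (Day 1"), so the factor is known for randomised subjects.

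**PASI90 is confirmatory.** Section 14.3.1.2 introduces its list with "All binary variables that are part of the testing hierarchy are given below", and PASI90 at Week 16 is the first entry. Figure 14-1 is not reproduced in the text available. The Amendment 1 log (Section 18.2, Change #35) places "PASI90 response at W16 superior to placebo" third, and the order in Section 4.2.1 agrees.

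**The models.** The binary secondary endpoints take over the methods of the primary endpoint. For those, Section 14.3.1.1 fixes only treatment and then says: "The suitability of including the randomization stratification variables, region and bone erosion at Baseline will be assessed and will be added to the model if" that is judged fitting. Section 14.3.1.2 makes an exception for outcomes of one kind: where the outcome "is an assessment of skin/dermatological manifestations of PsA the fitted model will exclude the fixed term bone erosion at Baseline". The sentence opens conditionally and gives PASI90 as an example, not as a closed list. For the continuous hierarchy endpoints the same section fixes an ANCOVA with treatment, bone erosion and region.

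**The hypothesis.** For binary endpoints, Section 14.3.1 says "the null hypothesis is that the conditional odds ratio is equal to one". It does not list the conditioning factors.

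**The concern.** A trial that restricts its randomisation by a factor would normally carry that factor into the analysis. Here one of two factors is removed by rule from a hierarchy test. The only reason on the page is that the outcome concerns skin. That is a view about whether erosion predicts PASI90, and the protocol offers no data on it.

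The choice is one-sided. If erosion does not predict PASI90, including it costs one parameter. If it does, leaving it out makes the test slightly less efficient and changes which odds ratio is reported, because odds ratios are non-collapsible. The same document keeps bone erosion for every continuous hierarchy endpoint, including SF-36 PCS, which is not a measure of joint damage. What is at stake is a little efficiency and a clear definition of the reported PASI90 odds ratio.

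**Working it through.** **Inputs from the protocol (Sections 14.9 and 14.9.2).** 420 bimekizumab and 280 placebo subjects; 60% with BSA ≥3%; PASI90 45% against 10%; two-sided α = 0.05; stated power >99%.

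**Step 1: reproduce the stated power.**
- Subjects analysed: 0.60 × 420 = 252 and 0.60 × 280 = 168.
- Pooled rate: (252 × 0.45 + 168 × 0.10)/420 = 130.2/420 = 0.31.
- Null SE: √[0.31 × 0.69 × (1/252 + 1/168)] = 0.0461. Alternative SE: √[0.45 × 0.55/252 + 0.10 × 0.90/168] = 0.0390.
- (0.35 − 1.96 × 0.0461)/0.0390 ≈ 6.7, so power exceeds 99.99%.
- The continuity correction reduces the effective placebo n to 168 × [1 − (1 + 1/1.5)/(2 × 168 × 0.35)]² ≈ 163. Power still exceeds 99.99%, so the plan's figure reproduces.
- Treatment odds ratio: (0.45/0.55)/(0.10/0.90) = 7.36.

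**Step 2: fit with and without bone erosion.** Simulated trials of 420 subjects, allocated 3:2 and balanced within erosion stratum, with a 10% placebo rate overall and logistic Wald tests. Each simulated trial was fitted both ways. Assumed, because the protocol gives neither: erosion-positive share 30% or 50%, and erosion–PASI90 odds ratio 1 to 3. Region was not simulated.

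Type I error in %, with / without the term (8,000 runs per cell; Monte Carlo SE about 0.24 points):

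| Erosion OR | 30% erosion-positive | 50% erosion-positive |
|---|---|---|
| 1 | 5.1 / 5.1 | 4.5 / 4.5 |
| 1.5 | 4.8 / 4.7 | 4.7 / 4.6 |
| 2 | 4.7 / 4.5 | 4.9 / 4.7 |
| 3 | 5.0 / 4.6 | 4.5 / 4.3 |

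Planned effect (true conditional OR 7.36), 50% erosion-positive, 2,000 runs. The odds ratio is the exponentiated mean log OR, followed by the mean SE of the log OR:

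| Erosion OR | With term | Without term |
|---|---|---|
| 1 | 7.62 (0.293) | 7.59 (0.293) |
| 1.5 | 7.70 (0.295) | 7.55 (0.293) |
| 2 | 7.59 (0.297) | 7.26 (0.293) |
| 3 | 7.60 (0.300) | 6.88 (0.292) |

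Every run was significant under both models. The adjusted values exceed 7.36 through small-sample bias, so the comparison to make is between columns. The SE is larger with the term, but the estimate rises by more. At an erosion OR of 3 the mean log OR divided by its SE is about 6.75 with the term (2.028/0.300) and about 6.6 without (1.929/0.292).

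A separate run of 1,500 trials per scenario with 40% erosion-positive agrees. With no erosion effect the SE is 0.293 with the term and 0.292 without. At an erosion OR of 2 the log OR falls from 2.03 to 1.98 when the term is dropped.

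**Step 3: size of the shift.** At an erosion OR of 2: (ln 7.59 − ln 7.26)/0.297 = 0.045/0.297 ≈ 0.15 standard errors. At an erosion OR of 3: (ln 7.60 − ln 6.88)/0.300 = 0.099/0.300 ≈ 0.33.

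**Step 4: a smaller effect, where power is not saturated.** With an assumed treatment OR of 2.2 and 50% erosion-positive (4,000 runs), power with / without the term is 77.2% / 77.1%, 76.8% / 76.2% and 75.5% / 74.2% at erosion ORs of 1, 2 and 3.

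**The case against.** The case for leaving the sentence alone has real force.

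- **The exclusion is pre-specified and has an evident clinical rationale.** This stands. It is not a data-driven choice, and region is not excluded.
- **Nothing in the protocol links erosion of hands and feet to skin clearance.** This also stands. With no association the two models are practically identical. That removes the case for harm, but it gives no reason to omit the term.
- **A reader might infer that PASI90 conditions on different factors from the other binary hierarchy tests.** The documents do not support this. Section 14.3.1.1 adds region and erosion only if judged suitable, and that rule carries to all binary secondaries, so they have no fixed conditioning set to differ from. The exclusion also does not contradict the conditional odds ratio hypothesis, because the conditioning factors are never named. The only firm contrast is with the continuous ANCOVA models.
- **A reader might call the smaller odds ratio biased.** It is non-collapsibility: the model without the term targets a less conditional odds ratio. The null of no effect is still validly tested.
- **The conservatism may be overstated.** PASI90 is analysed only in subjects with BSA ≥3%, which is not a stratification factor. Balance within erosion strata in that subset is therefore not guaranteed by design, as it was in the simulation. This stands, and it makes a small effect smaller.
- **Section 14.3.3 already plans PASI90 subgroups by bone erosion.** These can show whether the effect differs by stratum, but they do not replace an adjusted confirmatory test.

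**Conclusion.** The point holds as a minor weakness in efficiency and in analysing as randomised. The protocol takes a randomisation stratum out of the model for a hierarchy endpoint without a statistical reason, although the continuous hierarchy models keep it. Including the term is essentially free if erosion is irrelevant and slightly better if it is prognostic.

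A reader might go further and infer that the exclusion threatens type I error or the fixed sequence. The calculations do not support that. Without the term, simulated type I error ran from 4.3% to 5.1%, never above the value with the term, and PASI90 power is above 99% either way. The differences in estimate and power rest on assumed erosion shares and erosion odds ratios that the protocol does not give. No decision in the trial is expected to turn on this. It is a free improvement, desirable but not required.

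**What to change.** Replace the exclusion sentence in Section 14.3.1.2 with: *The logistic model for PASI90 and other skin responder endpoints will include treatment, region and bone erosion at Baseline as fixed effects.*

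Deletion alone would return PASI90 to the suitability rule in Section 14.3.1.1, under which both strata remain optional. If the sponsor prefers to leave erosion out, it should state the statistical reason and add an erosion-adjusted sensitivity analysis for PASI90.

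The cost is one sentence and one model parameter, set against about 130 expected responders. No new data are needed, because erosion is already read at Screening for the randomisation.
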